### 8.2.1.Total Sample Size

Total sample size is expected to be a a minimum total of 80 cases divided amongst the magnets from either one site or multiple sites.

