### 1.2. Study Rationale

Several hurdles which radiologists encounter specifically in MRI, are: acquiring the most amount of information; minimizing acquisition time; acquiring images with adequate quality; and standardization of the acquired images. Current neuroimaging protocols are in the realm of 20 minutes which include conventional T1-weighted, T2-weighted, T2 FLAIR imaging and/or Diffusion Weighted Imaging. The image quality depends on several factors including magnetic field strength, coils, image resolution and often differ depending on these factors from scanner to scanner.

The proposed STAGE imaging protocol (Strategically Acquired Gradient Echo) is a multipronged image acquisition and processing approach to address the aforementioned issues. Using specific collection parameters from a 3D gradient echo sequence, MRI scans can be performed for 3/1.5 Tesla magnets across most existing machines, independent of manufacturer. Upon data collection, the images are exported from the PACS archiving system and processed in our STAGE module to generate several weighted contrasts and quantitative maps, then returned to the PACS for radiologic review. All of the contrasts and quantitative maps are co-registered, 3D, and the same image resolution which makes for easy comparison between scans and manufacturers. Having quantitative maps provides source signal which mitigates bias between scanners. This protocol has great potential to decrease scan times, increase hospital and image center throughput, and also provide quality 3D images.

## 2. SUMMARY OF DEVICE DESCRIPTION .....

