### 4.2. Primary Endpoints

4.2.1. Primary Endpoint 1: each STAGE and MRI input or output is graded qualitatively by an experienced individual at the MRI center. Quality grading is performed on a 5-point scale [5=excellent; 4=good; 3=acceptable; 2=poor; 1=unacceptable] on several criteria [blurring/ghosting/ringing; flow artifact; intensity and homogeneity; signal to noise ratio; susceptibility artifacts]. For the questions with a 5-point score, the points will be averaged with scores  $\geq 3$  can be used for clinical diagnosis.

4.2.2. Primary Endpoint 2: contrast appearance will also be graded on a binary basis: passed, failed. All binary questions should have a 'Pass' answer will qualify as "Passed."

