## 8.2. Sample Size Justification

Up to one hundred twenty (120) subjects (aged 6-80 years) will be enrolled in this study, with an expected data attrition rate of 20% which may be due to poor data quality from motion artifact or withdrawal from the study. Eighty subjects, minimum, will provide at least 90% power (with two-tailed alpha of 0.05) to reject the null hypothesis that STAGE images have lower or equal score to conventional MRI images. This was calculated from a paired t-test which has a slightly higher sensitivity than a Wilcoxon-test. Differences of STAGE-scores and MRI-scores will be paired. For the power calculation I assume a mean difference of STAGE-score – MRI-score of 0.5 points with STD =1.

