## 8.3. DATA ANALYSIS AND REPORTING OF RESULTS

### 8.3.1.Analysis of Effectiveness Endpoints

- 8.3.1.1. Primary Endpoint 1: The score of each STAGE and MRI input or output across individuals will be analyzed using a Mann-Whitney tests.
- 8.3.1.2. Primary Endpoint 2: General image quality on a binary basis (passed, failed) will be required to pass in all cases where the input data was found to be clinically useable.

Alpha of  $p < 0.05$  will be considered significant.

## 9. ADVERSE EVENT REPORTING.....

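### Cases are spread over an unstated number of magnets, but the planned test pools all scores, unpaired and without a magnet term, so variation between scanners in the STAGE-minus-MRI difference would go unseen

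*Combined protocol and SAP*

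**What the plan says.** - **Allocation (8.2.1).** The minimum of 80 cases is "divided amongst the magnets from either one site or multiple sites". No section gives the number of magnets, sites or readers, or the split between 1.5T and 3T.
- **Settings (7.2).** Echo times, repetition time, flip angles and slice settings differ between 3T and 1.5T. They may also vary somewhat with the scanner's software version. The comparator scans use recommended parameters, with durations that depend on field strength.
- **Power (8.2).** "Eighty subjects, minimum, will provide at least 90% power" ("with two-tailed alpha of 0.05"). This comes from a paired t-test with a mean difference of "STAGE-score – MRI-score of 0.5 points with STD =1". There is no design effect.
- **Analysis (8.3.1.1).** The scores "across individuals will be analyzed using a Mann-Whitney tests", judged at p < 0.05. There is no magnet, site or reader term, no result by magnet and no confidence interval.
- **Intended reach (1.2, 3.2).** Section 1.2 says that image-quality factors "often differ depending on these factors from scanner to scanner" and that STAGE scanning can be done "across most existing machines, independent of manufacturer". Section 3.2 lists standardization across manufacturers and field strengths as a benefit to society.
- **Grading.** Under 4.2.1 images are "graded qualitatively by an experienced individual at the MRI center". Sections 1.1 and 8.1 speak of a neuroradiologist or radiologist in the singular.

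**The concern.** Each subject gives both a STAGE and a conventional image on the same magnet. A magnet effect common to both images cancels in the within-subject difference. What does not cancel is a magnet-by-method effect, where STAGE does relatively better on one scanner than on another. Section 7.2 makes this plausible, because the settings of both methods can change with the magnet.

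If the effect exists, differences from the same magnet are correlated. Eighty cases then carry less information about scanners in general than 80 independent pairs. One or two favourable magnets could also carry a pooled result, and nothing in the planned output would show it. If only one magnet is used, which the plan does not clearly exclude, variation between scanners cannot be estimated at all.

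**Working it through.** **Inputs from the documents:** n = 80 pairs, mean difference 0.5, SD of the difference 1, two-sided alpha 0.05 (8.2).

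**Assumed, because the documents give no values:** k = 2, 4 or 8 magnets of equal size; intraclass correlation (ICC) of the paired difference within magnet of 0.02 to 0.10; inference to magnets in general.

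**1. The plan's own figure.** The noncentrality is 0.5 × √80 = 4.47. The noncentral t with 79 degrees of freedom gives 99.3% power (normal approximation: Φ(4.47 − 1.96) = 99.4%). Exactly 90% needs 44 pairs. The stated figure of at least 90% is therefore true as a lower bound, with 80 − 44 = 36 pairs to spare.

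**2. Clustering in a paired test.** Design effect DE = 1 + (80/k − 1) × ICC; effective n = 80/DE; power = Φ(0.5 × √(80/DE) − 1.96); error of a paired test that ignores magnet = 2 × (1 − Φ(1.96/√DE)).

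| Magnets | ICC | DE | Effective n | Power | Error, magnet ignored |
|---|---|---|---|---|---|
| 2 | 0.02 | 1.78 | 45 | 92% | 14% |
| 2 | 0.10 | 4.90 | 16 | 52% | 38% |
| 4 | 0.02 | 1 + 19 × 0.02 = 1.38 | 58 | 97% | 10% |
| 4 | 0.05 | 1.95 | 41 | 89% | 16% |
| 4 | 0.10 | 1 + 19 × 0.10 = 2.90 | 28 | 75% | 25% |
| 8 | 0.02 | 1.18 | 68 | 98% | 7% |
| 8 | 0.10 | 1.90 | 42 | 90% | 16% |

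With ICC = 0 there is no effect.

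**3. How much clustering the 90% survives.** Setting 0.5 × √(80/DE) = 1.96 + 1.28 gives DE of about 1.90. That corresponds to an ICC of 0.90/39 = 0.023 with two magnets, 0.90/19 = 0.048 with four and 0.90/9 = 0.10 with eight. These use a normal reference. A t reference on k − 1 degrees of freedom, which suits inference to other magnets, is much less forgiving: at ICC 0.05, power is 16% (two magnets), 58% (four) and 89% (eight).

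**4. The test actually planned.** Mann-Whitney ignores pairing. Let ρ be the correlation between a subject's STAGE and MRI scores. With equal score variances and the SD of the difference held at 1, an unpaired comparison takes the variance of the mean difference to be 1/(80 × (1 − ρ)). The true value is DE/80. The ratio of true to assumed variance is DE × (1 − ρ), so the error is approximately 2 × (1 − Φ(1.96/√(DE × (1 − ρ)))). For four magnets and ICC 0.05 (DE 1.95):

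| ρ (assumed) | DE × (1 − ρ) | Approximate error | Mann-Whitney, simulated (2,000 runs) |
|---|---|---|---|
| 0 | 1.95 | 16% | 16% |
| 0.3 | 1.37 | 9% | 10% |
| 0.5 | 0.98 | 5% | 5.5% |
| 0.7 | 0.59 | 1% | 1% |

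The two effects balance at ρ = 1 − 1/DE = 0.49. Below that the planned test is too liberal; above it, too conservative. The documents give no value for ρ.

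**The case against.** The strongest objection is that the broad reach is not a hypothesis of this study. The phrase in 1.2 concerns where the sequence can be run, 3.2 lists a hoped-for benefit, and 4.3 defines success by clinically acceptable quality and expected contrasts. If inference is only to the magnets scanned, the design effect does not apply. That stands, and it is why the fix limits the conclusion instead of requiring a larger trial. It does not remove the need to show results by magnet, since a pooled score can hide a scanner on which STAGE does worse.

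A reader might also infer several stronger points that the documents do not support:

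- **That the planned p-value is too small.** The planned test is unpaired, and ignoring positive within-subject correlation works in the opposite direction. The net direction is unknown.
- **That an interval is too narrow.** The plan specifies no interval, only a p-value rule.
- **That the stated power is wrong.** The 80 pairs give about 99% and, on the normal approximation, tolerate a design effect of about 1.9. With eight magnets the 90% holds over the whole assumed ICC range.
- **That each magnet has its own grader.** Section 4.2.1 allows local graders, but 1.1 and 8.1 can be read as one radiologist. In that case there are no grader clusters, although agreement with other readers is untested.
- **That one site means one manufacturer.** A single site may hold several makes, and 8.2.1 speaks of magnets in the plural.

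**Conclusion.** The point holds in a limited form. Cases are grouped by magnet, settings can differ between magnets, and neither the power basis nor the planned test allows for this. The planned test also drops the pairing on which 8.2 relies. A STAGE-minus-MRI difference that varies by magnet would go undetected, and precision for scanners not studied would be overstated.

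The amount cannot be fixed from the documents. With four equal magnets and an ICC of 0.02 to 0.10, all assumed, a paired test has an effective sample size of 58 to 28 instead of 80. The possible offset from the unpaired test is accidental and is no safeguard: moving to the paired analysis that 8.2 describes would expose the clustering. The change is worth making before analysis, but nothing here shows the sample size to be inadequate for the magnets scanned.

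**What to change.** In 8.3.1.1:

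1. Replace the Mann-Whitney test with a paired analysis of the within-subject STAGE-minus-MRI difference, stratified by magnet, and by reader if there is more than one.
2. Report that difference with its 95% interval overall and for each magnet or field strength.
3. Limit the conclusion to the magnets and manufacturers scanned.

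In 8.2.1, state the number of magnets, sites and readers and the allocation by field strength, and reconcile the grader descriptions in 1.1, 4.2.1 and 8.1.

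The cost is SAP wording, slightly more analysis on data already held, and a narrower claim. Per-magnet intervals will be wide: with 20 cases and SD 1 the half-width is about 1.96/√20 = 0.44, so they describe consistency and are not separate tests.

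If a manufacturer-independent conclusion is wanted, magnet would have to be a random effect and the power restated with few degrees of freedom. That is a real trade-off: the between-magnet variance is barely estimable with two to four magnets and not estimable with one, so the broad claim could require more magnets.

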## 8.3. DATA ANALYSIS AND REPORTING OF RESULTS

### 8.3.1.Analysis of Effectiveness Endpoints

- 8.3.1.1. Primary Endpoint 1: The score of each STAGE and MRI input or output across individuals will be analyzed using a Mann-Whitney tests.
- 8.3.1.2. Primary Endpoint 2: General image quality on a binary basis (passed, failed) will be required to pass in all cases where the input data was found to be clinically useable.

Alpha of  $p < 0.05$  will be considered significant.

## 9. ADVERSE EVENT REPORTING.....

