### 1.1. Overview of Device/Procedure

The study objective is to validate STAGE images and, when applicable, their equivalence to conventional MRI through an assessment by a trained certified neuroradiologist in a clinical setting.

The data collected in this study will be utilized to support an FDA 510(k) submission to gain FDA clearance to market the FDA Class II STAGE system in the United States.

*This study does not involve comparing test subjects vs. control subjects, nor does it involve any treatment and follow-up.*

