### 4.3. Study Success

The study will be considered successful if STAGE data quality is found to be clinically acceptable and generated contrasts are as expected based on statistical testing.

## 5. CLINICAL STUDY DESIGN .....

This is prospective observational, non-interventional cohort study to evaluate the efficacy of the collection protocol and STAGE system processing algorithm. STAGE system output will be compared to the MRI output from the same patient.

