#### **MRI Scan**

Total study time which includes the patient intake and the scans may take up to two hours.

The subject will undergo a brain MRI scan using the STAGE Protocol\* either at 3 Tesla or 1.5 Tesla field strength. The STAGE protocol consists of two flow-compensated spoiled 3D gradient-echo multi-echo scans, run at different specific flip angles.

For 3T\*\* scan parameters are as follows: FOV: 256x192 mm, matrix size: 384x288 or 384x384, slices:  $\geq 64$ , slice thickness: 1.34mm and 2mm, TE= 7.5/12.5/17.5ms, bandwidth per pixel <240Hz, and TR=25ms. Two multi echo scans will be run: with FA = 6° and one with FA = 24°. Data will be collected with In-plane resolutions of 0.67x1.33mm and 0.67x1mm (freq dir x phase dir). Scanner options for partial fourier and elliptical sampling should be turned on if available. The total protocol time will be roughly 5 minutes.

For 1.5T\*\*, the scan parameters are: FOV: 256x192 mm, matrix size: 384x288 or 384x384, slices:  $\geq 48$ , slice thickness 2.7mm and 2mm, TE= 10/20/35ms, bandwidth per pixel <200Hz, and TR = 40ms. Data will be collected with in-plane resolutions of 0.67x1.33mm and 0.67x1mm (freq dir x phase dir). Two multi echo scans will be run: One with with FA of 7° and one with 35°.

Upon collection, the subject's raw DICOM files transferred to the PACS system and then manually sent by the user to the STAGE module for post-processing. (*note: the subject need not be present for this step*) The processed STAGE images will be sent back to the PACS system where they remain within the participant's scan folder and are clearly labeled. They can then be viewed at an integrated workstation. Original and temporary data linked to the patient will be deleted from the module after it is processed.

The generated contrasts are the following:

- Enhanced T1-weighted images (T1We)
- Susceptibility Weighted Images (SWI)
- T1 Maps
- Proton Density Maps
- R2\* Maps
- Susceptibility maps (SWIM)
- Pseudo and modified pseudo SWIM
- True SWI (tSWI)
- Dual inversion recovery images of the CSF, White matter, and Gray matter
- MRA
- Maximum or minimum intensity projections of SWI, tSWI, R2\*

Options for outputting sagittal and coronal reformatted images will be provided for the T1We and T1 maps. Additionally, all images will have an option for skull stripping as well as a 1x1x2 sliding window filter.

\*No contrast administration is required in this protocol.

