\*\* These parameters may vary slightly depending on the limitations of the scanner software version.

For the purposes of validation, additional data will be collected as a gold standard to compare with the STAGE inputs outputs. This includes 3D T1 MP-RAGE and proton density weighted imaging, which are to be collected at recommended parameters, but with similar FOV and matrix size to the images in the STAGE imaging protocol. Scan collection times will range from about 5 – 10 minutes, depending on the field strength.

The MD will be given a survey with questions concerning image quality, whether contrasts based on the tissue properties match the input and outputs, or if anatomical structures appear or not.

No biological specimens will be collected in this study. The study involves MR imaging. STAGE involves an Investigational medical device which is labeled for Investigational Use Only, per FDA IDE labeling requirements/research purposes only.

For children (subjects aged 6-17 years) involved in this study, headphones will be provided to ensure comfort. The subject may need to stay still for a time period up to 40 minutes. A sedative may be prescribed by the subject's primary physician to be taken prior to the scan to mitigate motion during the scan. This study will not involve any intravenous sedation. The subject will be informed that he or she can rest shortly between sequences (each sequence may last 5-10 minutes) if needed, and that the study can be stopped at any time if he or she needs.

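### Primary Endpoint 1 is to be tested with an independent-samples Mann-Whitney test, although the STAGE and MRI scores are paired within patient and the sample size rests on a paired test

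*Combined protocol and SAP*

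**What the plan says.** Section 8.3.1.1 is the only place that prescribes an analysis of Primary Endpoint 1: "The score of each STAGE and MRI input or output across individuals will be analyzed using a Mann-Whitney tests".

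The rest of the document describes paired data:

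- Section 5: "STAGE system output will be compared to the MRI output from the same patient".
- Section 1.1: "This study does not involve comparing test subjects vs. control subjects". Sections 5.1 and 5.2 give both the test arm and the control arm as not applicable.
- Section 8.2, on the sample size: "This was calculated from a paired t-test which has a slightly higher sensitivity than a Wilcoxon-test", followed by "Differences of STAGE-scores and MRI-scores will be paired" and "I assume a mean difference of STAGE-score – MRI-score of 0.5 points with STD =1". It claims a power of 90% or more from a minimum of 80 subjects at two-tailed alpha 0.05.

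On what is compared with what, section 7.2 (MRI Scan) introduces a long list of STAGE outputs with "The generated contrasts are the following". Of the additional scans collected as the reference it says: "This includes 3D T1 MP-RAGE and proton density weighted imaging".

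**The concern.** The Mann-Whitney test takes its null distribution from two unrelated sets of subjects. Here each patient contributes a score to both sets, so patient-level features that affect both images (motion, anatomy, scanner) are likely to move the two scores together. The test ignores that shared component and counts it as noise.

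Two things follow. First, the power in section 8.2 belongs to a different test from the one in section 8.3.1.1, so the plan does not show that its own analysis is adequately powered. Second, an analyst following 8.3.1.1 would run one test and an analyst following 8.2 another. For a primary endpoint, that leaves room to choose after the scores are known.

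The direction of the error matters too. A conservative test does not help a claim that STAGE scores higher. It does make it less likely that a real shortfall of STAGE would be detected, which is a weakness in a study whose stated objective includes equivalence to conventional MRI.

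**Working it through.** **Inputs.** From section 8.2: n = 80 pairs (the minimum), mean difference δ = 0.5, SD 1, two-sided alpha 0.05. From section 4.2.1: 5-point grades averaged over five criteria, so scores move in steps of about 0.2. Not in the documents: the within-patient correlation ρ, taken as an assumption over a range; and whether the SD of 1 belongs to the difference (likelier, given the wording of 8.2) or to each score. Both readings are shown.

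**Step 1: the plan's own figure.** Paired t-test, SD of the difference 1:
- Noncentrality = δ√n / SD = 0.5 × √80 / 1 = 4.47, with 79 degrees of freedom. Exact power is 99.3%. The normal approximation gives Φ(4.47 − 1.96) = Φ(2.51) = 99.4%.
- 90% power needs 44 pairs (exact paired t-test) or about 47 (signed-rank).

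The stated 90% is therefore true as a lower bound for a paired test.

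**Step 2: why the unpaired test is conservative.** If each score has SD σ, the difference in means has true variance 2σ²(1 − ρ)/n, but an unpaired test works with 2σ²/n. The effective critical value becomes 1.96/√(1 − ρ). For a test on means this gives a rough per-test type I error of:
- ρ = 0.3: 1.96/0.837 = 2.34, about 1.9%
- ρ = 0.5: 1.96/0.707 = 2.77, about 0.6%
- ρ = 0.7: 1.96/0.548 = 3.58, about 0.04%

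**Step 3: simulation of the planned test.** Correlated normal scores rounded to 0.2, 80 pairs, two-sided 0.05, 10,000 runs per cell (3,000 for signed-rank).

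Reading (a), SD of the difference 1, so σ = 1/√(2(1 − ρ)):

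| ρ | σ | Mann-Whitney type I error | Mann-Whitney power | Signed-rank power | Pairs for 90%, Mann-Whitney |
|---|---|---|---|---|---|
| 0.3 | 0.85 | 2.2% | 98% | 99% | 58 |
| 0.5 | 1.00 | 0.7% | 94% | 99% | 72 |
| 0.6 | 1.12 | 0.2% | 88% | 99% | 84 |
| 0.7 | 1.29 | 0.1% | 77% | 99% | 102 |

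Mann-Whitney power crosses 90% at ρ of about 0.58 (20,000 runs: 90.5% at 0.57, 90.0% at 0.58, 89.0% at 0.59). The type I error of the signed-rank test stays near 5% (4.5% to 5.7%). A per-score SD of 1.12 to 1.29 is large on a 1-to-5 scale, so the last two rows are outer bounds. Limiting scores to the range 1 to 5 leaves the picture similar: about 93% at ρ = 0.5 and 74% to 76% at ρ = 0.7.

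Reading (b), SD of each score 1:

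| ρ | Mann-Whitney type I error | Mann-Whitney power | Signed-rank power |
|---|---|---|---|
| 0 | 5.1% | 87% | 87% |
| 0.3 | 1.8% | 90% | 95% |
| 0.5 | 0.5% | 93% | 99% |
| 0.7 | 0.04% | 97% | 100% |

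**Step 4: is there a paired analysis elsewhere?** None was found, nor any other handling of within-patient correlation for this endpoint. Section 11.3 mentions recruiting controls, but section 5.2 gives the control arm as not applicable, so no independent group exists to which a Mann-Whitney test would apply.

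**The case against.** The best counter-case accepts the inconsistency and disputes its weight.

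- **The stated power mostly survives.** Under the likelier reading of the SD, it fails only above a correlation of about 0.58, where the implied per-score SD exceeds 1/√(2 × 0.42) = 1.09. Enrolment may also reach 120; with 20% attrition that leaves 120 × 0.8 = 96 pairs, and simulated Mann-Whitney power is then about 94% at 0.6 and 87% at 0.7. Under the other reading the shortfall is one to three points at low correlation, and at zero correlation the paired test has the same shortfall. This stands: a serious loss of power is possible but not shown. More pairs soften the loss; they do not make the test valid for paired data.
- **It may be a slip of the pen.** Section 8.2 mentions a Wilcoxon test beside paired differences, so a signed-rank test may have been meant, and sizing on a t-test while analysing by ranks is ordinary practice. This is plausible. But 8.3.1.1 is the operative instruction, it names the unpaired test, and a slip needs the same correction.
- **The type I statement is limited.** It applies per test and under positive correlation. Many outputs are scored, and nothing here bounds the study-wide error rate. This is right, and the conclusion is worded accordingly.
- **The comparator list goes beyond renaming a test.** In part. The reference scans in section 7.2 are introduced as inclusions, so the two named may not be all. Still, a paired difference exists only where the same patient has both images, so some statement of the pairs follows from pairing itself.

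**Conclusion.** The concern holds, with high confidence. The test named for Primary Endpoint 1 does not fit the data the study collects and is not the test that supports its sample size. This must be corrected before analysis because the primary test is wrong as written and conflicts with section 8.2; the case does not depend on a proven loss of power.

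The effect is conservative. Under positive correlation, per-test type I error drops from 5% to about 2% at a correlation of 0.3 and below 1% at 0.5. If 1 is the SD of the difference, power at 80 pairs lies between about 98% and 77% for correlations of 0.3 to 0.7, against about 99% for a paired test, with 90% retained up to about 0.58. If 1 is the SD of each score, Mann-Whitney power rises from about 87% at zero correlation to 97% at 0.7, at or below the signed-rank test throughout. These figures rest on an assumed correlation, normal scores rounded to 0.2, and a true difference of 0.5.

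**What to change.** 1. In 8.3.1.1, replace the Mann-Whitney test with the Wilcoxon signed-rank test (or the paired t-test of 8.2) on within-patient STAGE minus MRI differences, and report the paired difference with a 95% confidence interval.
2. State which STAGE output is paired with which conventional image, and limit the paired test to outputs that have a comparator in the same patient. Say how outputs without a comparator will be summarised.
3. In 8.2, name the same test as in 8.3.1.1 and say whether 1 is the SD of the difference. If it is, 80 pairs give about 99% power and the existing claim stands as a lower bound. If it is the SD of each score, give the assumed correlation as well.

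The cost is a changed test name, one clarifying phrase and a short list of pairs. The list needs a decision by the sponsor, but no extra subjects, scans or readings.
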